Title: Comparison of Etomidate Plus Propofol, Etomidate Alone on Induction of Anesthesia

NCT03820388

Document Date: March 15, 2017

1) **Protocol Title**

Comparison of Etomidate Plus Propofol vs. Propofol, Etomidate Alone on Induction of Anesthesia, a Pilot Observational Study

Protocol Version Date: 5/2/2017

2) Objectives

The purpose of this study is compare of etomidate plus propofol vs. propofol or etomidate alone during induction of anesthesia.

The specific aims or objectives are testing patient reactions during induction, and in the post anesthesia care unit (PACU).

The hypotheses to be tested: induction with etomidate combined with propofol when compared to induction with propofol or etomidate alone:

1. will provide less pain during injection,

2. less hypotension (compare to propofol), less hypertension (compare to etomidate) and better hemodynamics than propofol or etomidate during induction,

3. Similar postoperative nausea and vomiting (PONV) when compared with propofol and less PONV when compared with etomidate,

4. Similar pain score among all three groups

3) Background

Induction of anesthesia is a critical part of anesthesia practice. Sudden hypotension, hypertension, arrhythmias, and cardiovascular collapse are threatening complications following injection of induction agent in hemodynamically unstable patients. It is desirable to use a safe agent with fewer adverse effects for this purpose.

Both etomidate and propofol are the most commonly used induction agents for general anesthesia (GA) and both propofol and etomidate have their advantages and disadvantages. Propofol has been associated with injection pain, significant hemodynamic change (hypotension) during induction and less PONV. Etomidate has been associated with more stable hemodynamic and less pain during induction, but more myoclonic movements at induction and PONV. However, those findings are still controversial and the published results are still inconsistent.

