Systolic blood pressure, diastolic blood pressure, mean arterial pressure, heart rate will be monitored and recorded before induction, at induction and intubation followed by 1, 3, 5 and 10 minutes after intubation.

Pain on injection will be measured using 4 graded scale; 0 --- no pain, 1 --- verbal complaint of pain, 2 --- withdrawal of arm, 3 --- both verbal complaint and withdrawal of arm.

The incidence and degree of myoclonic movements also recorded as follows: 0 = no myoclonic movements, 1 = minor myoclonic movements, 2 = moderate myoclonic movements, 3 = major myoclonic movements.

The medications used in the 3 groups are clinically used already with FDA approval for their use. This is an observational study and we will compare the effects of the three groups with their medication uses on the parameters we listed above: systolic blood pressure, diastolic blood pressure, mean arterial pressure, heart rate, pain on injection, myoclonic movements, PONV and BIS numbers.

Non-English speaking participants are still eligible for the study. We will use translation services in line with HRP 090 and HRP 091 and the consent short form to enroll interested non-English speaking participants. If we find that we have enrolled 2 patients of a particular language using the short form as the study progressed, we will obtain full translation of the consent form into that language through the use of UCD Translation Services.

8) Data and/or Specimen Management and Confidentiality

All data will be summarized using descriptive statistics. Summaries of continuous variables will present mean, median, standard deviation, minimum, and maximum; summaries of categorical variables will present frequencies and percentages. All data will be presented in subject data listings.

Subject enrollment and disposition, including reasons for early withdrawal from the study, will summarized by group.

Demographic variables will be summarized by group for all enrolled subjects. Data will be stored up to 3 years after finishing the study.

This is a pilot study with a proposal to enroll 25 patients into each group for a total of 75 patients randomized.

We expect to complete data analysis on 20 patients in each group for a total of 60 patients due to patient withdrawal either voluntarily or due to formal withdrawal criteria, ie difficulty with securing patient airway.

9) Provisions to Monitor the Data to Ensure the Safety of Subjects

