Title: Comparison of Etomidate Plus Propofol, Etomidate Alone on Induction of Anesthesia

NCT03820388

Document Date: September 26, 2017

Statistical Analysis

Sample size calculations were based on our pilot study, and we found MAP to be 80.1 (± 10.3) mmHg, 90.3 (± 10.4) mmHg, 91.0 (± 11.6) mmHg in group P, PE and E at induction. Using PASS 15.0 software, a sample size of 20 patients per group would be needed to detect statistically significant differences with the power of 0.9 and the alpha level of 0.05. Considering a possible 20% dropout rate, 25 patients per group were recruited for the study.

Parametric values were expressed as mean (SD), or percentages of the total number of patients (%). Categorical data were analyzed using χ^2 or Fisher's exact test as appropriate. The hemodynamic parameters among the three groups were compared using the general linear model (GLM). We also considered time of evaluation as a within-subject factor, and the intervention state as a between-subject factor. The time groups (interaction terms) were considered group differences among the three groups in their responses over time. We used Mauchly's sphericity test for compound symmetry assumption. Differences in hemodynamic variables between the three groups at different time points were compared by post hoc Bonferroni test. $P < 0.05$ was considered statistically significant. All statistical analyses were performed with SPSS 22.0 (SPSS; Chicago, IL, USA).

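### The only SAP test that fits the 0–3 pain and myoclonus grades ignores grade order; naming an ordinal, pairwise analysis would be a cheap improvement to these secondary endpoints.

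*SAP*

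**What the plan says.** Protocol section 7 (Procedures Involved) defines both scales. For pain, "Pain on injection will be measured using 4 graded scale; 0 --- no pain", rising to grade 3 for complaint together with arm withdrawal. For myoclonus, "The incidence and degree of myoclonic movements also recorded as follows: 0 = no myoclonic movements, 1 = minor myoclonic movements", rising to moderate (2) and major (3). Section 6 lists both as secondary endpoints.

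Protocol section 2, hypothesis 1, says that the combination, compared with propofol or etomidate alone, "will provide less pain during injection". None of the four hypotheses concerns myoclonus.

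Protocol section 8 plans frequencies and percentages for categorical variables and names no test.

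The SAP names two families of test. One is a repeated-measures general linear model with Bonferroni post hoc comparisons, for haemodynamic variables. The other is: "Categorical data were analyzed using χ^2 or Fisher" (the exact test). The SAP does not mention the pain or myoclonus scales, does not say whether grades are kept as four categories or collapsed, and gives no pairwise comparisons for categorical outcomes.

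**The concern.** Hypothesis 1 is directional and pairwise: less pain than propofol, and less than etomidate. Pearson chi-square or Fisher on the four grades asks only whether the distributions differ in some way. It spends 3 degrees of freedom on a two-group table, or 6 on a three-group table, and part of these goes to patterns with no bearing on more or less pain. Relabelling the grades leaves its P value unchanged.

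Two things are at stake. A real reduction in pain is more likely to be missed. And because the SAP leaves four-grade, collapsed, three-group and pairwise analyses all open in a non-blinded trial, the choice could be made after the data are seen.

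**Working it through.** **1. The plan's own figure.** The documents state power only for mean arterial pressure: 20 per group, power 0.9, alpha 0.05.

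- SAP means 80.1, 90.3 and 91.0 have grand mean 87.13. The SD of the means is √[(7.03² + 3.17² + 3.87²)/3] = 4.98.
- Pooled SD = √[(10.3² + 10.4² + 11.6²)/3] = 10.78, so f = 4.98/10.78 = 0.462.
- One-way ANOVA power at 20 per group is 0.887 (21 are needed for 0.90). With SD 10.4 or 10.3 it is 0.909 or 0.915 at 20.
- 20/(1 − 0.2) = 25 recruited.

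The figure is reproduced to within one patient. It says nothing about pain or myoclonus.

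**2. Does the named test use the order?** Take illustrative counts for grades 0 to 3 of [4, 6, 8, 7] and [12, 7, 4, 2], 25 per group. Expected counts in each group are 8, 6.5, 6 and 4.5.

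χ² = 2 × (4²/8 + 0.5²/6.5 + 2²/6 + 2.5²/4.5) = 2 × 4.094 = 8.19 on 3 df, P = 0.042.

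Shuffling the grade columns leaves P = 0.042. The Wilcoxon-Mann-Whitney P moves from 0.005 to 0.86.

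**3. Power in one assumed example.** Assume propofol grades 40/25/20/15% and a common odds ratio of 4 favouring the combination. The cumulative odds 0.667, 1.857 and 5.667 become 2.667, 7.429 and 22.67, which gives 73/15/8/4%. Two groups, two-sided 0.05 (the SAP does not state sidedness), asymptotic tests, enumerating every possible table:

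| Test | 20 per group | 25 per group |
|---|---|---|
| Chi-square, four grades | 0.39 | 0.50 |
| Wilcoxon-Mann-Whitney, tie-corrected | 0.59 | 0.69 |
| Any vs none, uncorrected chi-square | 0.54 | 0.70 |
| Any vs none, Fisher | 0.42 | 0.59 |

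With no true difference, four-grade chi-square and Wilcoxon both reject in just under 5% of trials. The four-grade shortfall is 20 points at 20 per group and 19 at 25.

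**4. How far this depends on the assumptions.** The other assumed baselines were 25/25/25/25, 40/30/15/15, 60/20/10/10 and 30/30/20/20%.

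- Odds ratio 2.5 to 6: four-grade chi-square is roughly 11 to 25 points below Wilcoxon in simulation (12 to 26 by enumeration).
- Odds ratio 2: about 7 to 10 points.
- Odds ratio 10 to 15: about 1 to 14 points.
- Shift from grade 1 to grade 0 only (30/50/10/10% to 70/10/10/10%), 20 per group: chi-square 0.73, Wilcoxon 0.48. The rank test loses.
- Any vs none, uncorrected chi-square, odds ratio 3 to 6: about 0 to 12 points below Wilcoxon.
- Any vs none, Fisher, odds ratio 2 to 5: about 8 to 22 points below Wilcoxon.

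**5. With the two contrasts adjusted.** At 0.025 per contrast, the example in step 3 gives chi-square 0.27 and Wilcoxon 0.47 at 20 per group, and 0.37 and 0.58 at 25. The gap stays near 20 points, and absolute power is modest with either test.

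**The case against.** The strongest reply is that the SAP never assigns these scales to a test. The protocol records the incidence of myoclonus as well as its degree, and the SAP reports percentages, so a 2×2 comparison of any versus none fits the wording. On that reading an uncorrected chi-square costs about 5 points in the example at 20 per group and nothing at 25. This stands. It does not settle the matter: the collapse is not specified, Fisher does worse, and grades 1 to 3 are merged although the protocol distinguishes them.

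A reader might go further than the documents allow in four ways.

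- *That the scales can only be tested by chi-square or Fisher on four grades.* That is an inference. These are the only named tests that fit, but the coding of the grades is left open.
- *That the plan cannot show less pain.* Direction can be read from the planned percentages, and a two-sided Wilcoxon P value carries no direction either.
- *That a three-group chi-square is at fault because it can reject when only etomidate differs.* Any omnibus test does this. With the combination equal to propofol and an etomidate odds ratio of 4 to 5, chi-square rejects in about 39% to 62% of trials and Kruskal-Wallis, which uses the order, in about 60% to 82%. The remedy for that is pairwise contrasts.
- *That a fixed power loss follows from the plan.* No grade rates are given, and proportional-odds shifts favour rank tests.

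It is also fair that these are secondary endpoints in a self-described pilot, and that no stated hypothesis concerns myoclonus.

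**Conclusion.** The concern holds in a limited form. The only named test that could apply to the two graded scales ignores their order when used on four categories, and no pairwise contrast is specified for a hypothesis that is directional and pairwise. The loss of roughly 11 to 25 points rests on assumed baselines, a proportional-odds shift with odds ratio about 2.5 to 6, 20 to 25 per group and the four-grade reading. Outside those conditions it can be small or change sign. For myoclonus the point is only that recorded severity goes unused, since there is no directional claim to test. This is a cheap improvement to secondary endpoints, not a threat to the trial's main result: the sample size rests on blood pressure.

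**What to change.** Add to the SAP:

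- Analyse the 0–3 pain grade by tie-corrected Wilcoxon-Mann-Whitney with an exact P value, or by a proportional-odds model reporting the common odds ratio with 95% CI. Choose one before the data are seen.
- Make two contrasts, combination versus propofol and combination versus etomidate, with a Bonferroni adjustment for the two, in line with the SAP's haemodynamic comparisons.
- Apply the same ordinal method to the myoclonus grade, labelled as a secondary endpoint without a stated hypothesis.
- Keep chi-square or Fisher for binary items such as PONV yes/no.

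The cost is a few lines of SAP text, with no new data or patients. The Wilcoxon test uses only the grade order that the protocol already defines; the model also assumes a common odds ratio across cut-points. The downside is some loss of power if the true shift is confined to one pair of grades, so the full grade frequencies should be reported beside the test.

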Patients will be participating in the study for the duration of their surgery and for 24 hours after induction.

We anticipated it to take 1 year to enroll all study subjects.

We anticipate an extra 12 months after completion of the study for the investigators to complete the primary analyses.

6) Study Endpoints

The primary endpoints include:

- 1. Blood pressure changes during induction
- 2. Heart rate changes during induction

The secondary endpoints include:

- 1. Pain at injection
- 2. Myoclonic movements
- 3. PONV in PACU
- 4. Postoperative pain score
- 5. Incidence of adverse reactions during induction
- 6. Severity of adverse reactions during induction

7. Dose and frequency of vasoactive agents and other concomitant medications used to treat adverse reactions of propofol / etomidate

8. Sedation depth using bispectral index (BIS)

- 9. Eyelash reflex disappear time
- 10. Intubation time
- 11. Dose and frequency of analgesic and other sedatives used

7) **Procedures Involved**

This is a non-blinded, randomized, parallel-group study in patients scheduled for elective surgery under general anesthesia and orotracheal intubation to compare etomidate plus propofol vs. propofol or etomidate alone on induction of anesthesia.

There will be three cohorts of 25 patients per cohort with one cohort administered propofol, one cohort administered etomidate, and one cohort administered propofol

etomidate. The sample size was calculated with the blood pressure change \pm 20 mmHg, SD \pm 25 mmHg, power of 0.80 and p value of 0.05 and resulted 25 in each group.

The research team will create 75 envelopes. Each will be numbered, 25 will be in propofol group, 25 will be in etomidate group and 25 will be in propofol/etomidate group. On the day of surgery, one envelope will be randomly picked for each participant.

Patients in the three cohorts will be administered a 30 second bolus by manual hand push.

Intensive PD and safety assessments will be performed prior to dosing on Day 1 until 24 hours post-dose (Day 2). There are no plans for long-term follow-up past the 24 hours.

Three cohorts are as follow:

- 1. Propofol group: 2 mg/kg propofol
- 2. Etomidate group: 0.3 mg/kg etomidate
- 3. Propofol plus etomidate group: 1mg/kg propofol plus 0.15mg/kg etomidate.

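### The SAP's per-time pairwise comparisons ignore the pre-induction reading: valid under randomisation, but less precise than the recorded data allow

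*SAP*

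**What the plan says.** The design is randomised: "This is a non-blinded, randomized, parallel-group study in patients scheduled for elective surgery under general anesthesia and orotracheal intubation" (Protocol, section 7). The first primary endpoint is "Blood pressure changes during induction" and the second is the corresponding change in heart rate (Protocol, section 6). Section 7 lists systolic, diastolic and mean pressure and says that "heart rate will be monitored and recorded before induction, at induction and intubation followed by 1, 3, 5 and 10 minutes after intubation". That is one pre-treatment reading and six later ones.

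Hypothesis 2 (Protocol, section 2) is pairwise and directional. The combination is to give "less hypotension (compare to propofol), less hypertension (compare to etomidate) and better hemodynamics than propofol or etomidate during induction".

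The SAP analyses the haemodynamic variables with a general linear model: "We also considered time of evaluation as a within-subject factor, and the intervention state as a between-subject factor". On the interaction it says: "The time groups (interaction terms) were considered group differences among the three groups in their responses over time". The pairwise step is: "Differences in hemodynamic variables between the three groups at different time points were compared by post hoc Bonferroni test". Neither document names a baseline covariate or a change-from-baseline response for these analyses, and the SAP does not list the levels of its time factor.

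**The concern.** The endpoints are changes, but the comparisons that decide between pairs of groups are comparisons of levels. There are two readings of the SAP.

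- **Pre-induction is a time level.** The group-by-time term then does test whether change differs between groups. It is an omnibus term, however, and does not show which pair differs, when, or in which direction. The per-time comparisons that do show this make no use of the patient's own starting value.
- **Pre-induction is not a time level.** The analysis as written then does not use the reading at all.

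Under randomisation the groups have the same expected baseline, so a difference in levels, a difference in changes and a baseline-adjusted difference all have the same expectation. What differs is the variance. With about 20 analysed patients per group, chance baseline differences stay in the unadjusted comparison, and intervals are wider than necessary if baseline and outcome are moderately correlated. Because the three forms can differ materially in power, leaving the choice open also leaves room to choose after seeing the data.

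**Working it through.** **Inputs from the SAP.** MAP at induction: P 80.1 (SD 10.3), PE 90.3 (10.4), E 91.0 (11.6); 20 per group analysed, 25 recruited; power 0.9; alpha 0.05.

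**Assumptions.** Neither document gives the correlation ρ between pre-induction and induction MAP, so I use 0.1, 0.3, 0.5 and 0.7. The pre-induction SD is not given either; I set it equal to the pooled SD at induction. The Bonferroni multiplier is not stated; I take three pairs, so α = 0.05/3 = 0.0167, two-sided.

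**1. The plan's own figure.** Pooled SD = √[(10.3² + 10.4² + 11.6²)/3] = 10.78. A three-group F test on the SAP means has power 0.887 at 20 per group and reaches 0.9 at 21. Then 20/(1 − 0.2) = 25. The SAP's 20 and 25 are reproduced to within one patient, as an omnibus test on raw levels.

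**2. Unadjusted pairwise comparison, PE versus P, 20 per group.**
- Difference = 90.3 − 80.1 = 10.2 mmHg.
- SE = 10.78 × √(2/20) = 3.41 mmHg.
- Noncentrality = 10.2/3.41 = 2.99 on 57 df, critical t = 2.467.
- Power = 0.70; Bonferroni interval half-width = 2.467 × 3.41 = 8.4 mmHg.

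**3. The same comparison with baseline used.**
- Covariate adjustment: SE = 3.41 × √[(1 − ρ²)(1 + 1/55)], with one df lost.
- Simple change score with equal SDs: SE = 3.41 × √(2 − 2ρ).

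| ρ | Adjusted SE | Adjusted power | Adjusted half-width | Change-score SE | Change-score power |
|---|---|---|---|---|---|
| 0.1 | 3.42 | 0.69 | 8.4 | 4.57 | 0.41 |
| 0.3 | 3.28 | 0.74 | 8.1 | 4.03 | 0.53 |
| 0.5 | 2.98 | 0.83 | 7.4 | 3.41 | 0.70 |
| 0.7 | 2.46 | 0.95 | 6.1 | 2.64 | 0.91 |

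Unadjusted, for reference: SE 3.41, power 0.70, half-width 8.4.

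Adjustment breaks even where (1 − ρ²)(1 + 1/55) = 1, that is ρ = √(1/56) ≈ 0.13. At ρ = 0 it costs one point of power (0.70 to 0.69).

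With all 25 per group, unadjusted power is 0.81; adjusted power is about 0.81, 0.85, 0.91 and 0.98 at the same four correlations.

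**4. Omnibus test at 20 per group.** By simulation, power goes from 0.887 to 0.88, 0.91, 0.96 and 0.995.

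**5. Check of validity.** In 20,000 simulated trials per setting with no true difference, the unadjusted pairwise test rejected in 1.6–1.7% against a nominal 1.67%, and its estimate was unbiased. With the SAP's differences, simulated power agreed with the table (0.70 unadjusted; 0.74, 0.83 and 0.95 adjusted at ρ 0.3, 0.5 and 0.7).

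**6. Chance imbalance.** A pairwise baseline difference at 20 per group has SE 3.41 mmHg: median absolute value 0.6745 × 3.41 = 2.3 mmHg, 95% range ±1.96 × 3.41 = ±6.7 mmHg. With equal SDs, a fraction ρ of it carries into the unadjusted comparison. At ρ = 0.5 that is 1.15 mmHg at the median and 3.3 mmHg at the 95% limit.

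**The case against.** The strongest reply is that this is an efficiency preference and not an error. The SAP's analysis is valid, its size is correct, and the benefit rests on a correlation that the documents do not give. At ρ = 0.3, pairwise power moves only from 0.70 to 0.74 and the omnibus test, which is what reproduces the SAP's sample size, from 0.89 to 0.91. All of this stands, and it limits the point to precision.

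The protocol lists the pre-induction reading first in the same series as the others, so the time factor can naturally be read as including it, and the interaction then addresses change. That also stands, but it does not reach the per-time pairwise comparisons, which are unadjusted on either reading.

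The figures cover one contrast, one variable and one time point:
- For PE versus E the SAP's difference is 0.7 mmHg, and power is about 0.02 with or without adjustment.
- The documents give no means or SDs for heart rate, or for MAP at the later readings. Vasoactive treatment could weaken the correlation with baseline at those later times.

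The protocol's sizing statement ("The sample size was calculated with the blood pressure change", 20 mmHg with SD 25) is weak evidence of a planned change-score analysis. A plain two-group comparison of means reproduces its 25 per group: 2 × (1.96 + 0.84)² × 25²/20² = 24.5.

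Finally, the SAP is written in the past tense, so it may be too late to specify the adjustment in advance. That affects how the analysis is labelled, not whether it is useful.

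**Conclusion.** The point holds as a loss of precision, not of validity. On the SAP's own MAP figures, the unadjusted PE-versus-P comparison at 20 per group has power 0.70 and a half-width of 8.4 mmHg. Baseline adjustment brings no gain at ρ = 0.1, a small one at 0.3 and a clear one from 0.5, with a worst-case cost of about one point of power. These figures assume equal SDs before and at induction, three Bonferroni pairs and intact randomisation. Protocol section 17 allows withdrawals prompted by the assigned group, and baseline adjustment would not fully repair the effect of those. Adjustment does not help PE versus E at the SAP's difference. The improvement is worth making because the data are already collected, but it is not a defect that invalidates the plan. The SAP should state the role of the pre-induction reading whatever ρ turns out to be.

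**What to change.** State in the SAP that the pre-induction value is a covariate and not a response level. Model the six later readings with group, time, group-by-time, the patient's own centred pre-induction value of the same variable, and its interaction with time. For MAP at induction, the time point on which the SAP is sized, this is ANCOVA on pre-induction MAP. Report baseline-adjusted pairwise differences at each time with 95% confidence intervals, keep the Bonferroni correction, and state its multiplier.

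Do not replace this with simple change scores. With equal SDs they are less precise than raw levels when ρ is below 0.5. In general the break-even is ρ = SD(baseline)/(2 × SD(outcome)): about 0.37 for an assumed baseline SD of 8 mmHg and about 0.70 for 15 mmHg, against 10.78 at induction.

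If results have already been seen, report the adjusted analysis alongside the original and label it as added.

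The cost is a few lines of SAP text and one covariate in the software already named. It uses one between-subject degree of freedom and five within-subject degrees of freedom for baseline-by-time, and needs no further patients or measurements.

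### For injection pain and PONV the SAP plans no comparison of the combination with either single drug, so a significant categorical test need not bear on hypotheses 1 and 3

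*SAP*

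**What the plan says.** Protocol section 2 (Objectives) frames its hypotheses as "induction with etomidate combined with propofol when compared to induction with propofol or etomidate alone". Hypothesis 1 is that the combination "will provide less pain during injection". Hypothesis 3 is "Similar postoperative nausea and vomiting (PONV) when compared with propofol and less PONV when compared with etomidate". Each names a comparator, and every part except the claim of similar PONV has a direction.

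The SAP (Statistical Analysis) deals with categorical outcomes in one sentence: "Categorical data were analyzed using χ^2 or Fisher's exact test as appropriate". It names no contrast, effect estimate or multiplicity rule for them. Its one between-group follow-up is confined to haemodynamics: "Differences in hemodynamic variables between the three groups at different time points were compared by post hoc Bonferroni test". The significance threshold throughout is P < 0.05.

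Protocol section 8 adds only descriptive summaries, including frequencies and percentages for categorical variables. Section 6 lists injection pain and PONV as secondary endpoints. Section 7 grades injection pain from 0 to 3.

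Protocol section 3 (Background) already expects the single drugs to differ: "Etomidate has been associated with more stable hemodynamic and less pain during induction, but more myoclonic movements at induction and PONV". It adds that the published results are inconsistent.

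**The concern.** A chi-square or Fisher test on three arms asks whether any arm differs from any other. It has no direction and does not single out the combination. If propofol and etomidate differ from each other, as the background suggests for both pain and PONV, the test can be significant while the combination is no better than the drug it is meant to beat.

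The risk lies in interpretation. A reader who sees P < 0.05 for PONV may take it as support for less PONV than with etomidate, when the plan contains no test of that statement. The haemodynamic outcomes have a follow-up step that ties a difference to particular arms. Pain and PONV have none, although both are among the hypotheses the protocol says it will test.

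**Working it through.** **Arm sizes.** The SAP gives 20 analysed and 25 recruited per group, and 20/(1 − 0.20) = 25, as stated. The 20 is derived from mean arterial pressure (MAP):

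- Common SD = √[(10.3² + 10.4² + 11.6²)/3] = 10.78.
- The SD of the means 80.1, 90.3 and 91.0 about their average of 87.13 is √(74.45/3) = 4.98, so f = 4.98/10.78 = 0.462.
- A three-group ANOVA then has power 0.887 at 20 per group and needs 21 for 0.90. The stated 20 is reproduced to within one patient.

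The sample size is thus a MAP calculation and gives no event rate for pain or PONV. Every rate below is an assumption.

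**One data example, 20 per arm.** Suppose pain occurs in 12 propofol, 12 combination and 2 etomidate patients. The expected count per arm is 26/3 = 8.67 with pain and 11.33 without. The squared deviations sum to 3.33² + 3.33² + 6.67² = 66.7. Chi-square = 66.7/8.67 + 66.7/11.33 = 13.57 on 2 df, P = 0.001. The direct comparisons (two-sided Fisher) are combination versus propofol 12/20 v 12/20, P = 1.00, and combination versus etomidate 12/20 v 2/20, P = 0.002 in the direction opposite to hypothesis 1. The three-arm test is highly significant, and neither part of hypothesis 1 is supported.

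**How often this happens.** Each arm's count is binomial(n, p), with the outcome taken as any versus none. All combinations of the three counts were enumerated exactly. The probabilities of those with Pearson chi-square P < 0.05 (2 df) were summed, and likewise those in which a two-sided Fisher test at 0.05 favours the combination.

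PONV with the combination equal to etomidate, so that less PONV than etomidate is false:

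| Propofol / combination / etomidate | Three-arm test significant, n = 20 / 25 | Direct test wrongly favours combination over etomidate, n = 20 / 25 |
|---|---|---|
| 20% / 30% / 30% | 0.11 / 0.12 | 0.012 / 0.011 |
| 10% / 30% / 30% | 0.32 / 0.40 | 0.012 / 0.011 |
| 10% / 40% / 40% | 0.62 / 0.73 | 0.012 / 0.015 |
| 10% / 45% / 45% | 0.75 / 0.85 | 0.011 / 0.016 |

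Pain with the combination equal to propofol is the mirror image. For propofol and combination versus etomidate, the three-arm test is significant in 0.11 / 0.12 (30% v 20%), 0.32 / 0.40 (30% v 10%) and 0.96 / 0.99 (60% v 10%).

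As a check, with 30% in all three arms the three-arm test rejects in 0.052 / 0.050. The test itself is sound; it answers a different question from the one in the hypotheses.

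**The case against.** Several points on the other side are fair.

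- **The SAP does not call the test overall.** A reader might infer that it prescribes a single three-arm test and nothing else. It does not say so; that is only the most natural reading of one test for three groups. If pairwise tests were meant, the comparisons are unnamed and have no multiplicity control, so the gap remains in another form.
- **The P value is not the only evidence.** Both documents provide for percentages, so the rates of the combination and each single drug would appear side by side. That limits the scope for a wrong claim, but percentages alone give no interval or error control for the comparison a hypothesis names.
- **Myoclonus and adverse reactions.** They share the same SAP sentence, and it is tempting to include them. Neither is in a numbered hypothesis, so a significant result for them cannot mislead about hypotheses 1 and 3.
- **The size depends on assumed rates.** The higher percentages need large gaps between the single drugs. With a 10-point gap the three-arm test rejects in only 11% or 12%.
- **An intermediate result does not wholly refute hypothesis 1.** With pain at 60% propofol, 35% combination and 10% etomidate, the three-arm test is significant in 0.90 / 0.96 at 20 / 25 per arm. The combination is worse than etomidate but truly better than propofol, so half of the hypothesis holds.
- **Weight.** These are secondary endpoints of a self-described pilot, and the primary haemodynamic outcomes do have a follow-up comparison.

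These points narrow the claim and its size. None supplies the missing comparisons.

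**Conclusion.** The point holds for injection pain and PONV. The plan contains no inferential comparison of the combination with propofol or with etomidate on either outcome, and a three-arm P < 0.05 can reflect only the difference between the single drugs.

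Under the assumed PONV rates, with the combination no better than etomidate, the three-arm test is significant in 11% to 75% of trials at 20 per arm and 12% to 85% at 25. A direct test errs in favour of the combination in about 1 to 2%. The range rests on dichotomised outcomes and rates the documents do not give. The mismatch between test and hypothesis does not depend on those rates.

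A reader might go further and conclude that the trial is bound to report false support for its hypotheses, or that its sample size is undermined. The documents support neither: arm-level percentages will be reported, and the sample size concerns MAP. The change is worth making but is not critical to the primary analysis.

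**What to change.** In the SAP, base claims about injection pain and PONV on two pre-planned comparisons, combination versus propofol and combination versus etomidate, each with an effect estimate and 95% confidence interval.

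- **Injection pain:** choose in advance either any versus none or an ordinal comparison of the 0 to 3 grades. Apply Holm over the two comparisons, and claim less pain against a drug only if that comparison is significant in the stated direction.
- **PONV:** test combination versus etomidate directly. Report the combination-propofol difference with its interval, and do not infer similarity from a non-significant P value.
- **Three-arm P value:** keep it as descriptive.
- **Myoclonus and adverse reactions:** these may be reported in the same way, outside hypotheses 1 and 3.

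The cost is SAP wording, a few tables and some power for each pain claim. For pain at 35% combination versus 60% propofol, two-sided Fisher power falls from 0.23 at 0.05 to 0.19 at the first Holm step (0.025) with 20 per arm, and from 0.36 to 0.26 with 25. Power for that comparison is low either way, which is a further reason to report the interval.
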